## 5.2.3 Withdrawal from Trial Completely

The patient participant can withdraw consent at any time without providing a reason.

Patient participants who wish to withdraw consent for the trial will have pseudonymised data collected up to the point of withdrawal of consent included in the analyses.

Participants who withdraw from the trial completely will not contribute further data to the trial, unless this is required under applicable legislation (e.g. safety events) - the LCTC should be informed in writing and a withdrawal CRF should be completed.

Patient participants who have provided consent and been randomised, and whose surgeries are delayed beyond the agreed time-point for participation in the study will be withdrawn. This date will be advised to sites in advance. These participants will return to their normal clinical care pathway. They will not be replaced and follow-up data will not be collected.

**IRAS Ref: 271885** Page 34 of 89

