#### **Inclusion Criteria**

Potential patient participants eligible for the trial must comply with all of the following at randomisation:

- 1. Age 18 years and above
- 2. Undergoing a primary total hip arthroplasty with either a fully cemented or hybrid implant
- 3. Able to give informed consent prior to randomisation
- 4. Able to communicate in both written and spoken English

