#### **Exclusion Criteria**

Any patient participant meeting any of the criteria listed below prior to randomisation will be excluded from study participation:

- 1. Previous surgery to the hip joint.
- 2. All procedures with an indication other than osteoarthritis
- 3. Patient requiring complex total hip arthroplasty surgery, specifically augmentation of the acetabulum (e.g. structural bone graft or metal augment) and/or shortening/de-rotational osteotomy of the femur at the time of surgery.
- 4. Patients requiring bilateral simultaneous total hip arthroplasty
- 5. Vision impairment that precludes the completion of PROMS questionnaires.

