#### 7.3 Randomisation

Randomisation shall occur pre-operatively once the patient has been deemed eligible for the study, provided written informed consent and their baseline procedures completed. The randomisation sequence is pre-determined by LCTC, see section 11.1 for further details.

**IRAS Ref: 271885** Page 39 of 89

The randomisation will be processed using REDCap, a commercially available on-line research database system, and will be processed by the research team at the recruiting site. It should be completed as soon as possible for the purposes of operation list planning and implant procurement, and must be no later than the day prior to surgery. The only caveat to this deadline is for patients who will not be consented until the day of their surgery, in which case randomisation should be completed as soon as it is possible to do so.

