## 7.6 3-6 month post-op

Patient participants will be required to complete their PROMS questionnaires and healthcare resource use survey between 3 and 6 months postoperatively (from date of

**IRAS Ref: 271885** Page 40 of 89

surgery). This follow-up period will be dictated by the remaining duration of the study. All patient participation activity is expected to be completed by the end of October 20201. See the table below.

Month of Operation	Follow-up time point	Follow-up duration
January '21	July '21	6 months
February '21	August '21	6 months
March '21	September '21	6 months
April '21	October '21	6 months
May '21	October '21	5 months
June '21	October '21	4 months
July '21	October '21	3 months

PROMS questionnaires and a healthcare resource use survey will be sent in the post for the patient participant to complete. The accompanying cover letter will advise that the Oxford Hip Score is to be completed first, others are shown in a recommended order of completion of most recent recall period:

- Oxford Hip Score
- EQ-5D-5LTM
- Self-Administered Patient Satisfaction scale
- Forgotten Joint Score
- Work Productivity and Activity Impairment-Specific Health Problem
- Healthcare Resource Use Survey

A member of the hospital research team will contact the patient participants by phone before distribution to inform them of the upcoming postal questionnaires. The questionnaires should be posted early enough that the patient participant is in possession of them at the required 3-6 month post-operative date.

Patient participants will also be asked about any return to theatre required and any unanticipated contact with the surgical team or GP regarding the surgery.

The earliest that this data can be collected is 4 months postoperatively and the latest time is 8 months. Completion of these questionnaires outside of these parameters will be recorded as protocol deviations but will not affect the patients continuing participation in the trial.

Details on how and when to return the questionnaires are included within the covering letter.

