## 11.5 Analysis Plan

Feasibility and overall recruitment rate will be assessed at the opened sites by calculating the total number of patient participants randomised per month and the ratio of successful recruitment to eligible patients approached. Furthermore, observed recruitment rates, by site and overall, will be summarised along with a 95% confidence interval.

**IRAS Ref: 271885** Page 51 of 89

Much of the analysis will be performed using summary statistics and graphics. No formal assessments of efficacy, cost or safety across treatment arms will be made. All presentations of the data will take the form of summary analysis and graphical representations. Continuous data shall be presented using measure of median (interquartile ranges), whereas categorical data shall be presented in terms of frequencies of counts and associated percentages.

Primary and secondary outcomes will be compared between the two arms using a chisquared or Fisher's exact test.

All analyses shall be carried out on an intention to treat basis, retaining all patient participants in their initially randomised groups irrespective of any protocol deviations. The exception to this is the analysis of safety data which shall be analysed on the safety set which is defined by the type of arthroplasty that patients receive.

Feasibility of the study will be measured on the ability of the study to meet the recruitment targets and Stop/go criteria are defined on this basis.

Following 6 months of active recruitment, a target of 40 patient participants is set. If recruitment is  $\geq$  80% of this target ( $\geq$ 32 patients) a future full study can be considered feasible. If the observed recruitment rate is between 50% and 80% of the target (20-31 patients) then a future full study could potentially go ahead only if satisfactory measures can be taken to improve recruitment. Such measures must be realistic and have support of the study sponsor. If recruitment is less than 50% of the anticipated rate ( $\leq$ 19 patients) than the study won't be considered feasible to evolve into a full one in the future.

In addition, in order for the study to be considered feasible, it should not demonstrate any serious issues related to randomisation process, patient participant retention and/or protocol deviations.

Statistical analyses will be performed using a suitable recognised statistical software such as Stata v15 or above, R v3.3.0 or above and SAS v9.3 or above.

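### Section 5.2.3 ends all data collection for randomised patients whose surgery slips past the follow-up cut-off, although only the 3-month questionnaire is out of reach

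*Protocol*

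**What the plan says.** Section 5.2.3 deals with patients who have consented and been randomised but "whose surgeries are delayed beyond the agreed time-point for participation in the study will be withdrawn". On notice it says "This date will be advised to sites in advance", and on consequences "They will not be replaced and follow-up data will not be collected". The patients go back to their usual clinical pathway. The rule stands under the heading for complete withdrawal, where no further data are contributed unless legislation requires it.

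The calendar is in 7.6: "All patient participation activity is expected to be completed by the end of October" (the year is misprinted there, but the table beside it and the footnote to Table B give 2021). The last row of the table is a July 2021 operation with October 2021 follow-up at 3 months.

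The eligibility lists do not mention an operation date. The second inclusion criterion is "Undergoing a primary total hip arthroplasty with either a fully cemented or hybrid implant"; the others concern age, consent and English. The five exclusions, introduced by "Any patient participant meeting any of the criteria listed below prior to randomisation will be excluded from study participation", concern clinical indication, type of surgery and vision. On the timing of randomisation, 7.3 says "It should be completed as soon as possible for the purposes of operation list planning and implant procurement" and sets a latest time but no maximum interval to surgery. If surgery is more than 56 days after consent, 6.2 asks only for consent to be reaffirmed.

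Section 11.5 sets an intention-to-treat analysis "retaining all patient participants in their initially randomised groups irrespective of any protocol deviations".

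**The concern.** The rule is wider than its reason. A patient operated on after the cut-off cannot supply a 3-month questionnaire before the study ends. The rule nevertheless removes everything else as well: implant changes, length of stay, operation time, in-patient safety and the 6-week PROMS.

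These are not spare data. Section 2.3 lists cross-over during surgery, intra- and post-operative safety, follow-up capture and PROMS statistics among the objectives. Section 11.3 plans variance estimates for change at 6 weeks as well as at 3-6 months, from one longitudinal model of all data, so a patient with baseline and 6-week scores would contribute.

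The protocol takes the opposite line elsewhere. In 5.2, a patient who withdraws after surgery is asked to allow the scheduled assessments to continue. In 5.2.2, sites are asked to seek use of the routine 6-week data even when a patient no longer wants to complete PROMS. Under 5.2.3 a patient who is willing to carry on is not asked for the same data.

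There is also no check before randomisation that would keep foreseeable cases out. Sites will know the cut-off, but no criterion or randomisation step requires them to compare it with the listed operation date.

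**Working it through.** **Inputs.** Last operation month in the table: July 2021 (7.6). End of participant activity: end of October 2021 (7.6; Table B footnote). 6-week visit: nominal 42 days, earliest 3 weeks, latest 12 weeks after surgery (7.5). Surgical and in-patient data: during the stay (7.4). Target: 40 randomised (11.3).

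**The plan's own figures.** Follow-up in the 7.6 table should be the smaller of 6 months and the months left to October. For January to July this gives 6, 6, 6, 6, 5, 4 and 3 months, as printed. The recruitment rate in 11.3 is 40/(3 × 6) = 2.22 per site per month, as printed. That rate delivers exactly the 40 patients targeted, and 11.3 states no allowance for attrition.

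**Latest operation date for each type of data.** Assume a cut-off of 31 July 2021 and an end date of 31 October 2021.

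| Data | Calculation | Latest operation | Days after cut-off |
|---|---|---|---|
| 6-week visit, whole window to 12 weeks | 31 Oct − 84 days | 8 August | 8 |
| 6-week visit, nominal time | 31 Oct − 42 days | 19 September | 50 |
| 6-week visit, 3-week lower limit | 31 Oct − 21 days | 10 October | 71 |
| Surgical data | 31 Oct | 31 October | 92 |

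After 8 August the later part of the visit window is cut off by the end date. For the latest operations, a long hospital stay would also run past it.

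**Effect per patient.** Withdrawal is expressed on all randomised patients (11.2.2), so one patient is 1/40 = 2.5 percentage points. The protocol does not say how many might be affected. If 2 to 4 were (assumption), that is 2/40 = 5 to 4/40 = 10 points.

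**Effect on the variance estimates.** As an illustration, the 95% confidence interval for a standard deviation runs from √(df/χ²₀.₉₇₅) to √(df/χ²₀.₀₂₅) times the estimate, with df = n − 1.

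| Patients | Lower multiple | Upper multiple |
|---|---|---|
| 40 | 0.82 | 1.28 |
| 38 | 0.82 | 1.29 |
| 36 | 0.81 | 1.30 |
| 32 | 0.80 | 1.33 |

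Losing 2 to 4 patients widens the interval only slightly. The loss is avoidable, but it is not large.

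**The case against.** The rule is deliberate and addresses surgery that is delayed, that is, postponed. Sites receive the date beforehand, and 7.3 links early randomisation to planning the operating list, which suggests that most patients will already be listed. A date check would not stop a postponement that comes after randomisation. All of this stands, and it makes the problem smaller.

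Three stronger readings are tempting, and the protocol does not support them.

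- A reader might infer that 5.2.3 breaks the intention-to-treat rule. Section 11.5 governs the group in which patients are analysed. It does not forbid withdrawal or missing follow-up, and 5.2.3 does not remove these patients from any denominator. The two sections fit together poorly, but they do not contradict each other.
- A reader might infer that the feasibility decision is distorted. The numerical thresholds in 11.5 (32 and 20 patients) concern recruitment, which withdrawal after randomisation does not change. Retention enters only as a judgement about serious issues.
- A reader might infer that calendar withdrawals would be mistaken for patient choice. Section 11.2.2 already reports withdrawals by reason and stage for both arms, so they would be visible. Visibility does not recover the data, however.

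One further objection has weight. Once a patient has returned to the normal pathway, the protocol does not say whether the allocation still applies at the later operation. Cross-over can be interpreted only if that is stated. This does not affect the case for collecting safety and 6-week PROMS data.

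**Conclusion.** The point holds in a limited form. For willing randomised patients whose surgery is postponed past the cut-off, 5.2.3 gives up obtainable data: 6-week PROMS for operations up to about 19 September 2021 (10 October using the lower limit of the window), and surgical and in-patient safety data for operations up to 31 October. It does not follow that every delayed patient could be followed; after October 2021 nothing is obtainable within the study period.

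This rests on two assumptions: that the cut-off is the end of July, inferred from the 7.6 table, and that activity ends on 31 October 2021. The number of patients affected is unknown, so the 5 to 10 points of withdrawal are illustrative. A change is worth making because it is cheap, and because a 40-patient study with no stated attrition allowance has few observations to spare.

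**What to change.** 1. In 5.2.3, for randomised patients who still consent and whose surgery is delayed past the cut-off, replace the end of data collection with continued collection of surgical, in-patient, safety and 6-week PROMS data on the existing CRFs up to the end of October 2021. Analyse these patients in their randomised group, and record the 3-6 month questionnaire as not due rather than missing.
2. Have sites check, before randomising, that the listed operation date falls on or before the advised cut-off.
3. Reconcile 5.2.3 with 5.2, 5.2.2 and 11.5, and state whether the allocation still applies to a delayed patient. That last question is for the sponsor and the investigators; no answer is proposed here.

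The cost is protocol wording and CRF completion at a visit that is routine anyway. Patient blinding has to be kept for a few more people until their 6-week visit, and a few patients without a date will be randomised later. The check cannot prevent postponement after randomisation, which is why the first change is needed as well as the second.

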## 6 CONSENT AND ENROLMENT

Patient participants are undergoing elective total hip arthroplasty. With the exception of the type of implant used being selected by randomisation, all surgical and medical examinations, procedures and tests are as per routine care.

Some or all of the following questionnaires require completing at different time points of the study.

- Oxford Hip Score (OHS) (https://www.ncbi.nlm.nih.gov/pubmed/10158596)
- EuroQol 5 Dimension, 5 Level Quality of Life Questionnaire (EQ-5D-5L™) (https://www.ncbi.nlm.nih.gov/pubmed/21479777)
- Self-administered Patient Satisfaction scale (SAPS) (https://www.hindawi.com/journals/arthritis/2011/591253/)
- Forgotten Joint Score (FJS) (https://www.ncbi.nlm.nih.gov/pubmed/22000572)
- Work Productivity and Activity Impairment-Specific Health Problem (WPAI-SHP)
  - (https://www.ncbi.nlm.nih.gov/pubmed/10146874)
- Healthcare resource use survey (Bespoke to HipHOP)

# 6.1 Screening

A pseudonymised screening record of those patients identified a being potentially eligible to participate in Workstream 1 is to be maintained, regardless of whether they accept or decline.

The screening log will be made available via the REDCap database to sites that are open to recruitment.

### 6.2 Consent

Consent must be obtained before any trial specific procedures are carried out.

To assist with the approach method and consenting procedures, decision trees follow later in this section. These are for guidance only and can be flexible to complement existing procedures at the recruiting site.

Note: Consent will need to be reaffirmed if surgery does not occur within eight weeks (i.e. 56 days) of it most recently being given. The day on which consent was most recently given is day 0. Reaffirmation of consent does not require completion of an informed consent form, but is to be recorded within the patient notes.

If the patient declines the opportunity to participate, the site research team will record their reasons for refusal on the screening log. Decliners are not obliged to provide a reasons for non-participation, however efforts to elicit their reason for not participating should be made and recorded.

**IRAS Ref: 271885** Page 35 of 89

#### 6.2.1 Patient's identified in clinic

Once eligibility has been confirmed, and the patient's interest in the study also confirmed by an orthopaedic surgeon named on the delegation log, an Investigator or other appropriately trained member of the research team, e.g. Health Professional or Trial Administrator, will provide the patient with a REC approved Patient Information Sheet, plus a comprehensive verbal explanation of the study before discussing the trial with the patient. Throughout the consent process, potential patient participants will be encouraged to ask questions and will be reminded that they can withdraw at any time without their clinical care being affected. If the patient is willing to participate in the trial, consent can be obtained immediately after the discussion.

# 6.2.2 Patient's identified from operation waiting list – with time to PIS by post

Potential patient participants that are identified from operation waiting lists will be telephoned by a member of the direct care team to ascertain their basic interest in being involved in the study. Subsequently, and if the patient is interested, their details will be passed to the research team, who will post a copy of the Patient Information Sheet, with an introductory covering letter, to them in advance of a more detailed discussion by telephone. This telephone conversation must follow the same structure as a face-to-face discussion (see previous paragraph). The obtaining of consent from these patients will be deferred until their next hospital appointment. If their next appointment happens to be their day of surgery, consent can only be obtained prior to the patient receiving general anaesthetic or other medication that may reduce their capacity to understand the purpose of the Informed Consent Form.

# 6.2.3 Patient's identified from operation waiting list – without time to PIS by post

[figure not shown]
Potential patient participants that are identified from operation waiting lists will be telephoned by a member of the direct care team to ascertain their basic interest in being involved in the study. Subsequently, and if the patient is interested, their details will be passed to the research team. As the patient's operation is imminent, it will be explained to the patient that they will be approached by a member of the research team on their day of surgery who will discuss the study in more detail with them. Consent can only be obtained prior to the patient receiving general anaesthetic or other medication that may reduce their capacity to understand the purpose of the Informed Consent Form.

# 6.3 Loss of Capacity after providing consent

Should a patient lose capacity during the study they will be withdrawn from any future participation. See section 5.2 for further details.

[figure not shown]
**IRAS Ref: 271885** Page 36 of 89

Decision Tree 1 – Patient identified at a surgical clinic appointment

**IRAS Ref: 271885** Page 37 of 89

Decision Tree 2 - Patient identified from a THA operation waiting list

**IRAS Ref: 271885** Page 38 of 89

## 7 PARTICIPANT TIMELINES AND ASSESSMENTS

#### 7.1 Co-enrolment Guidelines

Patient participants in Workstream 1 of the HipHOP trial should not be recruited to other similar studies of hip replacement surgery. Similarly, patient participants already participating in other trials of total hip replacement should not enter Workstream 1 of the HipHOP trial.

If a participant is only taking part in Workstream 2 of the HipHOP study, they can be recruited to other studies of hip replacement surgery.

Any queries should be addressed to the trial coordinator.

## 7.2 Screening / Baseline

These procedures can occur on separate occasions or on the same day if required.

Screening procedures involve identifying and consenting the patient participant. See section 5.1 and section 6 for further details.

Baseline procedures can be done any time after consent has been obtained but must be completed prior to the patient being randomised. If baseline procedures are not completed until the day of surgery, they must also be completed prior to the patient participant receiving surgery related anaesthetic or other associated medication that may affect their ability to complete them accurately.

Note: All baseline procedures will need to be repeated if surgery does occur within eight weeks (i.e. 56 days) of their completion. The day of completion is day 0.

PROMS questionnaires to be completed are listed below. The Oxford Hip Score is to be completed first, others are shown in a recommended order of completion of most recent recall period:

- Oxford Hip Score
- EQ-5D-5L™
- Forgotten Joint Score
- Work Productivity and Activity Impairment—Specific Health Problem
- Healthcare Resource Use Survey

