## 7.11 Quality of Life and Health Economics

Health Related Quality of Life and Health Economics outcomes measures

Health-related quality-of-life (HRQL) and other outcomes for use in the health
economics component of the study will be assessed using the following
questionnaires:

- Oxford Hip Score (OHS)
- EuroQol 5 Dimension, 5 Level Quality of Life Questionnaire (EQ-5D-5L™)
- Self-administered Patient Satisfaction scale (SAPS)
- Forgotten Joint Score (FJS)
- Work Productivity and Activity Impairment-Specific Health Problem (WPAI-SHP)
- Healthcare Resource Use Survey

Baseline data will be collected prior to the patient participant being randomised, with further collections at 6 weeks and 3-6 months post-operation. The only exclusions to this are the Health Resource Use Survey data, which is only collected at baseline and 3-6 months post-operation and SAPS data, which is not collected at baseline and will only be collected at 6 weeks and 3-6 months post-operation.

- The Oxford Hip Score© is used to assess joint-specific pain and functional limitations encountered by the patient participant in day-to-day activities over the preceding 4 weeks.
- EQ-5D-5L™ is a preference-based HRQL measure comprising five domains, each with five levels. HRQL scores can be attached to each of the possible 3125 health states it describes.
- Self-administered Patient Satisfaction scale is a tool to measure patient satisfaction with their operation, pain, and ability to do daily activities and recreational activities.
- The Forgotten Joint Score is a 12 question scale used to measure joint awareness. It has been extensively validated to assess outcomes after total hip arthroplasty.
- Work Productivity and Activity Impairment-Specific Health Problem records data on work time and productivity over the preceding 7 days.
- The Healthcare Resource Use Survey is a HipHOP specific questionnaire

**IRAS Ref: 271885** Page 44 of 89

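### The baseline-repeat rule in Section 7.2 has its condition reversed; once corrected, it still conflicts with baseline-before-randomisation for patients already randomised when surgery slips past 56 days

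*Protocol*

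**What the plan says.** **Repeat rule (Protocol 7.2).** "All baseline procedures will need to be repeated if surgery does occur within eight weeks (i.e. 56 days) of their completion". The count starts at completion: "The day of completion is day 0". Five instruments are listed at baseline: the Oxford Hip Score (OHS), EQ-5D-5L, the Forgotten Joint Score (FJS), WPAI-SHP and the Healthcare Resource Use Survey.

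**Consent rule (Protocol 6.2).** Same window and same day-0 convention, opposite condition: "Consent will need to be reaffirmed if surgery does not occur within eight weeks (i.e. 56 days) of it most recently being given".

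**Order of baseline and randomisation.** Section 7.2 says baseline procedures "must be completed prior to the patient being randomised". Section 7.3 makes randomisation conditional on the patient having "provided written informed consent and their baseline procedures completed". Section 7.11 repeats the order: "Baseline data will be collected prior to the patient participant being randomised".

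**Timing of randomisation (Protocol 7.3).** "It should be completed as soon as possible for the purposes of operation list planning and implant procurement", and it "must be no later than the day prior to surgery". The exception is patients consented on the day of surgery.

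**Delay is foreseen.** Section 5.2.3 deals with randomised patients whose surgery is delayed beyond a cut-off. Section 7.12 deals with suspension of elective surgery.

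**The concern.** The repeat rule can only be meant to keep the pre-operative scores recent at the time of surgery. The printed sentence does the reverse. It is also a live instruction to sites. The General Information section rules out waivers and records non-compliance as protocol deviations, Section 11.2.2 counts deviations as a secondary outcome, and Section 11.5 makes the absence of serious deviation problems part of the feasibility judgement. A site that follows the evident intent departs from the text, and a site that follows the text cannot comply.

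Restoring the missing word does not settle everything. Consent can be reaffirmed after randomisation without difficulty. Baseline is different, because three sections place it before randomisation and none exempts a repeat.

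The baseline feeds the change in patient-reported outcomes (11.2.2), the variance of change that is to size the full trial (11.3), and the QALY calculation (10.2). The QALY interval runs from baseline collection to follow-up, so the choice of baseline alters both the starting utility and the time interval.

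**Working it through.** No sample size, power or alpha is involved. The check is one of logic, applied to the gap *g*, in days, from baseline completion (day 0) to surgery.

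**Inputs.** Window and day count from 7.2; parallel rule from 6.2; order of baseline and randomisation from 7.2, 7.3 and 7.11; randomisation limits from 7.3. I read a surgery on day 56 as within the window. The other reading moves the boundary by one day and changes no conclusion.

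**Step 1. The plan's own figure.** 8 weeks × 7 = 56 days. It reproduces.

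**Step 2. Rule as printed (repeat if g ≤ 56) against the rule with *not* restored (repeat if g > 56).**

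| Gap g (days) | As printed | With *not* restored |
|---|---|---|
| 0, 1, 14, 28, 55, 56 | repeat | keep |
| 57, 70, 84, 112 | keep | repeat |

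The printed rule is the exact complement of the intended one.

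**Step 3. Can the printed rule be met?** Take surgery at gap g ≤ 56 and a repeat done r days before surgery, with 0 ≤ r ≤ g. Then r ≤ 56, so the repeat itself meets the trigger and must be repeated. This holds for every g from 0 to 56 and every r from 0 to g. No sequence of repeats satisfies the rule. It also catches patients who complete baseline on the day of surgery (g = 0).

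**Step 4. Does the corrected repeat fall after randomisation?** With surgery on day s, a patient consented before the day of surgery may be randomised on any day from 0 to s − 1. That gives s permitted days, of which days 0 to 56 make 57.

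| Surgery on day s | Permitted randomisation days | Of these, on or before day 56 |
|---|---|---|
| 57 | 57 | 57 |
| 70 | 70 | 57 |
| 84 | 84 | 57 |
| 112 | 112 | 57 |

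For surgery on day 57, every permitted randomisation day comes before the 56 days have passed. For later surgery, a repeat prompted by the window running out precedes randomisation only if randomisation was held back beyond day 56. A repeat prompted by an earlier notice of delay precedes it only if that notice came before randomisation. These are counts of permitted days, not of patients. Because 7.3 asks for prompt randomisation, the default order is baseline, randomisation, delay, repeat.

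**Step 5. Is that order allowed?** Sections 7.2, 7.3 and 7.11 give no exception for a repeat, and no section says that the first baseline alone meets the requirement. The protocol therefore asks for a repeat and, on its face, forbids it at the time when it would usually be due.

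**The case against.** **This is an obvious slip.** Section 6.2 shows the intent, and because the printed sentence cannot be carried out, sites are unlikely to apply it literally. That is fair as to cause and likely conduct. It does not make the text correct, and the sentence governs site procedure and deviation reporting.

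**A reader might infer that all 40 participants would complete five extra questionnaires.** The documents do not support this. It assumes that sites apply an impossible rule, and that every operation falls within 56 days of baseline, an interval the protocol does not give.

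**A reader might infer that baseline age has no limit.** It has no limit of its own, but it is bounded. Section 5.2.3 withdraws randomised patients whose surgery passes the agreed cut-off and collects no follow-up from them. The table in 7.6 lists operations from January to July 2021 only, with follow-up closing in October.

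**A reader might infer that every corrected repeat falls after randomisation.** That goes too far: Section 7.3 allows randomisation up to the day before surgery, so a repeat can come first.

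**The first baseline already satisfies the requirement, and a repeat is only a refresh.** This is a reasonable reading and probably the workable one, but the protocol does not state it.

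**The choice between two baselines belongs in the analysis plan.** Agreed. Section 11.5 promises a separate plan, so its absence here is no fault. Whether a site may collect baseline after randomisation is a matter of conduct and belongs in the protocol.

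**The consequence is small.** Largely so. The primary outcome is recruitment, Section 11.5 disclaims formal comparison of efficacy, cost or safety, and Section 10.5 calls the cost per QALY indicative. A repeat before surgery comes from a patient who is to be kept blinded (Section 9) and has received neither implant, so bias should be limited, although the site research team processes the allocation (7.3).

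**Conclusion.** The point holds in two parts. First, the condition in 7.2 is reversed, contradicts the parallel rule in 6.2 and cannot be satisfied as printed. This rests on the text alone. Second, with *not* restored, the protocol still conflicts with itself, but only for patients already randomised when the 56 days pass or the delay becomes known. This rests on the default sequence in 7.3 and on the delay that 5.2.3 foresees.

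The number of patients in the second group cannot be derived from the protocol. The effect is confined to secondary material: change in patient-reported outcomes, its variance for planning the full trial, indicative QALYs and deviation counts. The recruitment outcome and its numerical stop/go thresholds are untouched. The correction is still worth making, because the rule is operational and costs almost nothing to put right.

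**What to change.** 1. In Protocol 7.2, insert *not* between *does* and *occur*, so that the baseline rule has the same condition as the consent rule in 6.2.
2. Add one sentence to 7.2: the original baseline satisfies the requirement that baseline precede randomisation, and a repeat before surgery is permitted after randomisation and is not a deviation. Cross-refer to it from 7.3 and 7.11.
3. In the analysis plan, fix in advance which baseline serves for change scores and for QALYs when a patient has two. The protocol need not prescribe the choice. Taking the last set before randomisation as a blanket rule would keep, in delayed patients, the out-of-date scores that the repeat is meant to replace.
4. Notify sites.

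Cost: one word, one sentence, two cross-references, a line in the analysis plan and a site notice, through the usual amendment route. No change to the sample size, the instruments or the visit schedule.
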